Official Study Title: *The Effect of Virtual Reality on Pain and Patient Satisfaction in Adults Receiving Genicular Nerve Radiofrequency Ablation*

NCT Number: NCT05468398

Date: April 23, 2025

Study Protocol

Study Title

The Effect of Virtual Reality on Pain and Anxiety in Adults Receiving Genicular Nerve Radiofrequency Ablation

Principal Investigator

[name], MD
Department of Anesthesia and Perioperative Care
University of California, Irvine
Email: [contact]
[contact]

Sponsor

University of California, Irvine

1. Background and Rationale

This study aimed to investigate whether Virtual Reality (VR) therapy could reduce procedural pain and anxiety in adults undergoing genicular nerve radiofrequency ablation (GNRFA). The study utilized the SootheVR system, a medically curated immersive VR device, during the procedure. VR therapy has emerged as a promising non-pharmacologic adjunct for managing procedural discomfort and anxiety.

2. Study Objectives

Primary Objective:

- To evaluate the effect of VR therapy on post-procedural pain levels using the Visual Analog Scale (VAS).

Secondary Objectives:

- To assess pre- and post-procedure anxiety scores.
- To measure patient satisfaction with the procedure.
- To assess provider satisfaction and perception of patient pain.
- To determine the use of additional local anesthetic.

3. Study Design

This was a randomized, non-blinded, single-site interventional study. Participants undergoing GNRFA were randomized to either receive standard care alone or standard care plus VR therapy using the SootheVR headset. Surveys were administered before and after the procedure to collect pain, anxiety, and satisfaction scores. Data were entered via Qualtrics.

4. Eligibility Criteria

Inclusion Criteria:

- Adults \geq 18 years
- Undergoing genicular nerve radiofrequency ablation
- Ability to consent

Exclusion Criteria:

- Need for sedation during procedure
- Cognitive impairment
- Neurological contraindications (e.g., epilepsy)
- Refusal or intolerance to VR headset
- Pregnancy
- Motion sickness, visual/auditory impairments affecting headset use

5. Study Procedures

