Participants were screened and consented on the day of the procedure. Baseline pain, anxiety, and prior VR experience were recorded via survey. Participants were then randomized to either VR or control group. Standard GNRFA was performed using fluoroscopy guidance. The VR group used the SootheVR headset during the procedure. Post-procedure, surveys captured outcome data including pain, anxiety, and satisfaction metrics.

6. Statistical Analysis Plan

Data were analyzed using descriptive statistics and comparative tests. Paired t-tests or Wilcoxon signed-rank tests were used to evaluate changes in pain and anxiety scores. Group comparisons were conducted using independent t-tests or Mann-Whitney U tests where applicable. Significance was set at $p < 0.05$.

7. Data Management

Data were entered into Qualtrics and exported to secure institutional drives for analysis. No protected health information was stored outside of secure UCI systems. Only authorized personnel had access to the data. Surveys and raw data were retained for IRB compliance and results reporting.

8. Ethics and Oversight

This study was reviewed and approved by the University of California, Irvine Institutional Review Board (IRB #2020-6207). All participants gave informed consent. Data confidentiality was maintained throughout the study. The study was minimal risk and included monitoring for adverse reactions to VR technology.

9. Study Status

The study has been completed. Enrollment and data collection are finalized. Results analysis is underway and will be submitted to ClinicalTrials.gov.

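### Section 6 commits to a p-value for the group comparison of VAS pain, but not to a VR-minus-control difference with a confidence interval

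*Combined protocol and SAP*

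**What the plan says.** Section 2 makes the effect of VR on VAS pain after the procedure the primary objective, and Section 3 describes a randomized comparison of standard care with and without the headset.

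Section 6 is four sentences long. It opens in general terms: "Data were analyzed using descriptive statistics and comparative tests". For change over time, "Paired t-tests or Wilcoxon signed-rank tests were used to evaluate changes in pain and anxiety scores". The last two sentences cover the comparison of arms and the threshold: "Group comparisons were conducted using independent t-tests or Mann-Whitney U tests where applicable. Significance was set at $p < 0.05". They do not say whether tests are one- or two-sided.

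The document names no between-arm effect measure, no confidence interval, no rule for choosing between the parametric and rank tests, no sample size or power, and no VAS difference regarded as important. It does not say which of the listed tests answers the primary objective. Section 5 records baseline pain before randomization, but Section 6 does not use it in any between-arm model.

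Section 9 states that "Enrollment and data collection are finalized" and that analysis of the results is in progress.

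**The concern.** The primary objective is about an effect, which needs a size and a precision. An analyst who follows Section 6 to the letter can finish with a summary for each arm and a p-value, and never state how many VAS points separate the arms or how well that number is known.

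Two misreadings then become easy. If p is 0.05 or more, the result may be reported as VR not reducing pain when the data still allow a worthwhile reduction. With no planned sample size in the document, the reader cannot fall back on design power to judge this. If p is below 0.05 from a rank test, benefit may be claimed with no statement of how much.

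The 0.05 threshold also covers the paired tests. A within-arm change, significant or not, does not estimate the effect of VR. Because Section 6 does not tie one test to the primary objective, nothing in it prevents a paired p-value from being presented as the main answer.

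**Working it through.** **Inputs from the document.** Two randomized arms (Section 3); VAS pain after the procedure (Section 2); significance level 0.05 (Section 6). There is no planned figure to reproduce.

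**Inputs assumed.** A 0-10 VAS, a common SD of 2.5 points (range 2 to 3), 1:1 allocation, a two-sided 95% interval, and 10 to 100 patients per arm. The document gives none of these.

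**Step 1: precision.** Half-width = t(0.975, 2n−2) × SD × √(2/n).

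| n per arm | t(0.975, 2n−2) | √(2/n) | SD 2.0 | SD 2.5 | SD 3.0 |
|---|---|---|---|---|---|
| 10 | 2.101 | 0.447 | 1.88 | 2.35 | 2.82 |
| 20 | 2.024 | 0.316 | 1.28 | 1.60 | 1.92 |
| 30 | 2.002 | 0.258 | 1.03 | 1.29 | 1.55 |
| 50 | 1.984 | 0.200 | 0.79 | 0.99 | 1.19 |
| 100 | 1.972 | 0.141 | 0.56 | 0.70 | 0.84 |

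If the observed difference favours VR but is not significant, it lies between 0 and one half-width, so the upper limit of benefit lies between one and two half-widths. At 20 per arm and SD 2.5, that is between 1.60 and 2 × 1.60 = 3.20 points.

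**Step 2: one p-value, two meanings.** Take a two-sided p of 0.40 and SD 2.5. The observed difference is t(0.80, 2n−2) × SD × √(2/n). Positive values favour VR.
- 10 per arm: 0.862 × 1.118 = 0.96; interval 0.96 ± 2.35, or −1.39 to 3.31.
- 100 per arm: 0.843 × 0.354 = 0.30; interval 0.30 ± 0.70, or −0.40 to 1.00.

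The first interval allows a benefit above 3 points; the second excludes anything above about 1 point. The 0.05 rule treats the two alike.

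**Step 3: chance of missing a real benefit.** For an assumed true benefit of 1.5 points, SD 2.5 and 20 per arm, the noncentrality is 1.5 / (2.5 × 0.316) = 1.90 on 38 degrees of freedom. Power is 45.6%, so p would be 0.05 or more 54% of the time.

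**Step 4: cost of the unstated choice of test.** Null simulations (8,000 trials each) used rounded 0-10 scores that were normal, skewed or floor-heavy, with 15 to 50 per arm. Rejection rates at a nominal 5% were:
- t-test alone: 4.7-5.5%
- Mann-Whitney alone: 4.3-5.2%
- whichever of the two was favourable: 5.3-6.4%
- test chosen by a Shapiro normality pre-test: 4.5-5.6%

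Even the worst behaviour adds about 1 point of type I error (6.4 − 5.0 = 1.4 at the extreme). Choosing by a normality check adds essentially nothing.

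**The case against.** The strongest reply is that Section 6 does plan descriptive statistics. If n, mean and SD are reported for each arm, anyone can compute the difference and an unadjusted interval. That stands, and it means a null result would not necessarily be uninterpretable. What remains is that Section 6 does not say which descriptive statistics will be given; medians reported with a Mann-Whitney p-value would not allow the interval to be derived.

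It is also fair to say that every figure above rests on an assumed n, SD and scale. The figures illustrate the problem and do not measure it in this trial.

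Three stronger readings are tempting, and the document does not support them.

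- A reader might infer that the test was picked after seeing the data. Section 6 does not say when or how tests were chosen, and its qualifier could refer to outcome type, since the group comparisons may also cover satisfaction and provider ratings. The rule is unstated; that does not show it was applied post hoc.
- A reader might argue that the rank test would mislead if only some patients respond to VR, because it can reject when means are equal. If some patients improve and the rest do not change, the means are not equal. In a simulation with rounded 0-10 scores, SD 2.5 and half the VR arm improving by 3 points, Mann-Whitney and Welch rejected at nearly the same rate: 37% and 38% at 20 per arm, 52% and 53% at 30, 75% and 75% at 50.
- A reader might conclude that a mean difference is the only acceptable estimate. That is partly preference; a Hodges-Lehmann shift with its interval also gives an effect in VAS points.

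**Conclusion.** The point holds as a gap in what the plan commits to reporting. Followed as written, Section 6 need not produce the size or precision of the effect that the primary objective asks about, and nothing elsewhere in the document fills the gap. With SD between 2 and 3 on a 0-10 scale, the unreported uncertainty would be roughly ±0.8 to ±1.2 points at 50 per arm and ±1.9 to ±2.8 at 10 per arm. How serious this is here depends on the actual sample size and SD, which the document does not give.

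The unstated choice between t-test and Mann-Whitney is a minor part of the point, worth about 1 point of type I error at worst. The missing estimate and interval carry the case. The change should be made, because it affects how the main result is read and can still be made while analysis is in progress.

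**What to change.** 1. Make the primary result one between-arm estimate of post-procedure VAS with a 95% CI: for example, the VR-minus-control mean difference with unequal-variance errors, adjusted for the recorded baseline pain. State that this comparison, and not the paired tests, answers the primary objective.
2. Report the Mann-Whitney test with the Hodges-Lehmann shift and its CI as a labelled sensitivity analysis.
3. Give n, mean and SD for each arm whichever test is quoted.
4. Date the change and label it as set after data collection and not prespecified. Editing Section 6 silently would make a late choice look planned.
5. State a VAS difference that matters, with its justification, and say that it too was set after data collection. Report p ≥ 0.05 as benefit not shown. Claim no important benefit only if the whole interval excludes that difference.

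The cost is some SAP wording, one regression model and one more column in the results table; no new data are needed. The downside is that a wide interval may look less favourable than a bare p-value.
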